#### 7.6 Medical History and Concurrent Medical Conditions

Summaries of medical history (significant conditions or diseases that stopped at or prior to the time of informed consent) and concurrent medical conditions (significant ongoing conditions or

diseases present at the time of informed consent) will be based on the Safety Analysis Set. No inferential statistics will be presented.

Medical history and concurrent medical conditions will be coded using the Medical Dictionary for Drug Regulatory Activities (MedDRA), Version 20.0 MIXED coding system.

Medical history and concurrent medical conditions will be summarized by system organ class (SOC) and preferred term (PT) for each treatment group. The tables will be sorted in alphabetic order by SOC and in decreasing frequency based on the total number of subjects in each PT. The number and percentage of subjects with any significant medical history and concurrent medical conditions will be summarized for each SOC and PT. The denominator used for calculating the percentages will be the total number of subjects included in each treatment group. For the tables, if a subject reports the same PT multiple times, then that PT will be counted only once for that subject. Similarly, if a subject reports multiple conditions within the same SOC, then that SOC will be counted only once for that subject.

A similar summary table will be provided for the ABPM subgroup.

All medical history and concurrent medical condition data will be listed.

## 7.7 Medication History and Concomitant Medications

Summaries of medication history and concomitant medications will be based on the Safety Analysis Set. No inferential statistics will be presented.

Medication history information to be obtained includes any medication relevant to eligibility criteria and efficacy/safety evaluation stopped at or within 28 days prior to signing of informed consent.

Concomitant medications are recorded on the eCRF and include any medication other than study drug taken at any time between time of informed consent through the end of the study (including the follow-up visit).

Medication history and concomitant medications will be coded using the World Health Organization (WHO) Drug Dictionary Version 01March2015 Enhanced coding system.

Medication history and concomitant medications will be summarized by treatment and preferred medication name. Preferred medication names will be sorted by decreasing frequency based on the total number of subjects.

Concomitant medications will be summarized separately according to the following subgroups:

- Concomitant medications that started and stopped prior to baseline. This includes any
  medication that was stopped after the time of informed consent and prior to the first dose of
  double-blind study medication.
- Concomitant medications that started prior to and were ongoing at baseline. This includes
  any medication that started before and was not stopped prior to the first dose of double-blind
  study medication.

- Concomitant medications that started after baseline. This includes any medication that started at or after the first dose of double-blind study medication.
- Concomitant medications that were ongoing at baseline and those that started after baseline.
  This includes any medication that started before and was not stopped prior to the first dose of
  double-blind study drug as well as any medication that started at or after the first dose of
  double-blind study medication.

Similar summaries will be provided for the ABPM subgroup.

Separate listings for medication history and concomitant medications will be presented by site and subject number.

## 7.8 Study Drug Exposure and Compliance

The duration of exposure to double-blind study medication is defined as date of last dose of double-blind study drug - date of first dose double-blind study drug + 1. The date of last double-blind dose will be obtained from the eCRF. In the event that the date of last dose is missing, the last dose date will be estimated as the later date between the last drug dispense date plus the number of days in the dosing interval (dispense date + next visit day – last visit day + 1) and the last study visit day for analysis and summary purposes.

The duration of exposure to double-blind treatment will be summarized by treatment group as a continuous variable and tabulated using following categories: 1 to 7 days, 8 to 14 days, 15 to 21 days, 22 to 28 days, 29 to 35 days, 36 to 42 days, 43 to 49 days, 50 to 56 days, 57 to 63 days and 64 days or more.

Subjects are to take 2 tablets for TAK-491 (40 mg/80 mg) and matching placebo or 2 capsules for valsartan and matching placebo each day. Overall percent study drug compliance for the double-blind treatment period will be calculated as:  $100 \times [\text{(number of tablets dispensed - number of tablets returned)}/(\text{expected number of tablets to be taken)}], where the expected number of tablets to be taken = [4*(date of last dose of medication - date of first dose of medication + 1)]. Compliance will be presented to 1 decimal place in the derived dataset.$ 

Overall double-blind study drug compliance will be summarized using descriptive statistics and by the number of subjects in each of the following compliance categories: <70%, 70 to 130%, >130%. A missing category will also be included, if applicable.

The summary of study drug exposure and compliance will be based on the Safety Analysis Set. No inferential statistics will be presented.

The above tables will also be provided for the ABPM subgroup. A compliance for ABPM procedure will be provided. The number and percentage of subjects with qualified ABPM recordings will be summarized by treatment group and overall at baseline and Week 8.

All study drug administration (single-blind placebo and double-blind study drug) and accountability data will be listed by site and subject number.

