6.0 STUDY DESIGN AND DESCRIPTION

6.1 Study Design

This is a phase 3, multicenter, randomized, double-blind, parallel-group study to evaluate the efficacy and safety of TAK-491 compared with valsartan over an 8 week treatment period in Chinese subjects with essential hypertension (trough, sitting clinic SBP \geq 150 and \leq 180 mm Hg on Day 1). This study will be conducted in China at approximately 20 to 25 sites and will include approximately 600 randomized subjects.

Before initiation of treatment, all subjects will participate in a 2-week, single-blind, placebo run-in period (Days -14 to -1). Subjects who have not received antihypertensive treatment within 28 days before screening can be entered into the run-in period as soon as all inclusion and exclusion criteria, including laboratory results, have been verified. Subjects taking previous antihypertensive agents will be required to participate in a 3-week washout/placebo run-in period (Days -21 to -1). If the subject's previous antihypertensive treatment includes amlodipine or chlorthalidone, then the washout/placebo run-in must be extended to 4 weeks (Days -28 to -1). Screening (Visit 1) will be scheduled before the washout/run-in period begins so that laboratory test results can be reviewed and subject eligibility can be confirmed before other treatments are stopped or placebo is initiated. At Day -14 (Visit 2), subjects will receive the first dose of single-blind placebo in clinic.

[figure not shown]
At Day 1 (Visit 5), eligible subjects will be randomly assigned to one of the following 3 groups with a 1:1:1 ratio:

- TAK-491 40 mg QD.
- TAK-491 80 mg QD.
- Valsartan 160 mg QD.

Subjects will be given the first dose of randomized study drug in the clinic at Day 1 (Visit 5). The last dose of randomized study drug will be taken the day of Week 8 visit (Visit 9). End of study assessment will be taken at Week 8/Early Termination (Visit 9). All subjects who receive study drug (placebo or double-blind) will be required to have a follow-up telephone call at approximately 14 days after the last dose.

A schematic of the study design is included as Figure 6.a.

V=visit, N/A=not applicable, D=day, HTN=hypertension, Wk=week, ET=Early Termination.

- (a) The Screening Visit should be scheduled before the washout/run-in period begins so that laboratory tests results can be reviewed and subject eligibility can be confirmed before other treatments are stopped or placebo is initiated.

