- (b) Subjects may be notified by telephone to begin the washout period.
- (c) Subjects taking previous antihypertensive agents are required to participate in a 3-week washout/run-in period (Days -21 to -1).
- (d) If the subject's previous antihypertensive treatment includes amlodipine or chlorthalidone, then the washout must be extended to 4 weeks (Days -28 to -1).
- (e) The first dose of placebo will be taken at the clinic on Day -14 (Visit 2).
- (f) Subjects who have not received antihypertensive treatment within 28 days prior to Screening can be entered into the run-in period as soon as all inclusion and exclusion criteria, including laboratory results, have been verified.
- (g) Last dose of double-blind is the day of Week 8/Final clinic visit or ET (Visit 9). And, in subgroup of ABPM subjects will start 24-hour ABPM measurement.
- (h) The follow-up telephone contact should be made approximately 14 days after the last dose.
- (i) Visit 4 only applies to ABPM subgroup subjects; start 24-hour ABPM measurement.
- (j) Visit 10 only applies to ABPM subgroup subjects.

A schedule of assessments is provided in Appendix A.

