9.3.7 Week 8/Final Visit or Early Termination (Visit 9)

Subjects should fast for 8 hours before this visit. Assessments scheduled for Week 8/ET (Visit 9) should be completed (safety permitting) for subjects who were randomized and withdraw early. The following procedures will be performed and documented:

- Clinic dosing at 8:00 AM (\pm 2 hours) and immediately prior to ABPM start (in subgroup only).
- Start 24-hour ABPM (in subgroup only).
- Vital signs (including standing measurements) and weight.
- Physical examination.
- 12-lead ECG.
- Concomitant medications.
- AE assessment.
- Collect double-blind study medication and assess subject compliance with dosing regimen.
- Access the IVRS/IWRS to register subject completion/early termination.
- Clinical laboratory tests (hematology, chemistry, and urinalysis), HbA1c, plasma renin concentration and activity, plasma and urine aldosterone, urine albumin and urine creatinine. Estimated GFR and UACR will be calculated by the central laboratory.
- Serum pregnancy test (female subjects of childbearing potential only).
- Guidance on avoidance of pregnancy, ova donation, and acceptable methods of contraception (female subjects of childbearing potential only).

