## 7.3 Analysis Sets

The following analysis sets will be used for analysis and presentation of the study data:

**The Randomized Set** will consist of all subjects who were randomized. For subjects who were randomized more than once, only the first randomization is used.

The Safety Analysis Set will consist of all subjects who received at least one dose of double-blind study medication. Subjects will be analyzed according to the study medication they received. Subjects who were randomized more than once are excluded from the Safety Analysis Set.

The Full Analysis Set (FAS) will consist of all randomized subjects who received at least one dose of double-blind study medication. A subject in FAS will be included in the analyses of a specific variable only when there is both a baseline value and at least one value during the double-blind treatment period. Subjects will be analyzed according to the treatment group to which they were randomized. Subjects who were randomized more than once are excluded from the Full Analysis Set.

The Per Protocol Set (PPS) will consist of all subjects in the FAS, excluding those who meet following criteria:

- 1. Subjects with SBP <150 mm Hg on Day 1.
- 2. Subjects who take study drug of a different treatment from the one randomized.
- 3. Subjects who are randomized more than once.
- 4. Subjects with a significant protocol deviation impacting baseline blood pressure.
- 5. Subjects with compliance outside of the range 70%-130%.
- 6. Subjects that took a prohibited medication potentially impacting baseline or Week 8 blood pressure.

Additional criteria may be identified prior to unblinding. If so, the additional criteria will be finalized and documented prior to database lock. Subjects who are included in the FAS but excluded from the PPS will be summarized for each criterion by treatment groups and overall. These subjects will also be presented in the listings.

The Ambulatory Blood Pressure Monitoring Set (ABPM Set) will consist of the subset of FAS subjects who received an ABPM recording at baseline. Subjects who have ABPM endpoints at both baseline and at least one post dose value will be included in all ABPM related summaries and analyses. Subjects who were randomized more than once are excluded from the ABPM Set.

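### The SAP fallback for a missing last-dose date can place the last dose after the study drug was collected

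*SAP*

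**What the plan says.** SAP 7.8 takes the date from the case report form first: "The date of last double-blind dose will be obtained from the eCRF". Only if it is missing does a fallback apply: "the last dose date will be estimated as the later date between the last drug dispense date plus the number of days" that separate two visits. The same sentence gives the formula for that first candidate and names the second: "dispense date + next visit day – last visit day + 1) and the last study visit day for analysis and summary purposes". Nothing limits the result to the ET visit, the drug return or a discontinuation date, and the SAP does not say whether the next visit day is the scheduled or the actual one.

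The protocol fixes when dosing ends. The design section states "The last dose of randomized study drug will be taken the day of Week 8 visit (Visit 9"), and note (g) to the study schematic extends this to early termination: "Last dose of double-blind is the day of Week 8/Final clinic visit or ET (Visit 9"). Section 9.3.7 lists at that visit: "Collect double-blind study medication and assess subject compliance with dosing regimen". It applies the visit to early withdrawals: "Assessments scheduled for Week 8/ET (Visit 9) should be completed (safety permitting) for subjects who were randomized and withdraw early".

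The date is used elsewhere. The compliance denominator in SAP 7.8 is four units per day from first to last dose. SAP 7.3 excludes from the per-protocol set (PPS), under criterion 5, "Subjects with compliance outside of the range 70%-130" (per cent).

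**The concern.** Two features of the fallback push the date late. Taking the later of the two candidates means that a subject who stops partway through an interval is credited with the whole interval, although the drug has been handed back. The added 1 is a separate off-by-one: an inclusive count of days is right for a duration, as in the exposure formula in the same section, but adding it to a start date overshoots by a day.

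A late date lengthens exposure and inflates the compliance denominator, so an adherent early withdrawal can look noncompliant and lose PPS membership. It also widens every window tied to the last dose: the 7-day limit in SAP Table 7.a, the 7-day limits for laboratory, vital-sign and ECG summaries, and the 14-day and 30-day adverse event windows. The error falls mainly on early withdrawals.

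**Working it through.** The documents state no figure that depends on this rule, so there is none to reproduce. The check applies the rule to each dispensing interval.

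**Inputs**
- Scheduled visit days 1, 14, 28, 42 and 56 (SAP Table 7.a).
- Drug dispensed on Day 1 and at Weeks 2, 4 and 6 (Protocol 8.1.3).
- Four units per day, two tablets and two capsules (SAP 7.8, Protocol 8.1.3).
- Assumption: a fully adherent subject whose true last dose is on the ET visit day *d*.

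**Formulas**
- Imputed day I = max(D + N − L + 1, V), with D the last dispense day, N the next visit day, L the last (dispensing) visit day and V the last study visit day.
- Compliance = 4d / [4 × (I − 1 + 1)] = d / I.

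**Reading A: N is the scheduled next visit**

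| Dispensed | First candidate | ET days dated late (excess) | ET days below 70% |
|---|---|---|---|
| Day 1 | 1 + 14 − 1 + 1 = 15 | 2–14 (13 down to 1 day) | 2–10 (10/15 = 66.7%; 11/15 = 73.3%) |
| Day 14 | 14 + 28 − 14 + 1 = 29 | 15–28 (14 down to 1) | 15–20 (20/29 = 69.0%; 21/29 = 72.4%) |
| Day 28 | 28 + 42 − 28 + 1 = 43 | 29–42 (14 down to 1) | 29–30 (30/43 = 69.8%; 31/43 = 72.1%) |
| Day 42 | 42 + 56 − 42 + 1 = 57 | 43–56 (14 down to 1) | none (43/57 = 75.4%) |

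Example, ET on Day 18: imputed Day 29, 11 days late. Compliance is (4 × 18)/(4 × 29) = 72/116 = 62.1% where the true value is 100%. The laboratory window runs to Day 29 + 7 = 36, which is 18 days after the true last dose. The 14-day adverse event window runs to Day 29 + 14 = 43, which is 25 days after it.

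**Reading B: N is the actual ET visit**

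With D = L and N = V = d, I = d + 1, always one day after collection. ET on Day 18 gives Day 19 and 18/19 = 94.7%. The ratio d/(d + 1) is below 70% only at d = 2 (2/3 = 66.7%); at d = 3 it is already 75%.

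**Completers**

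Dispensed on Day 42 and seen on Day 56: Day 57 under either reading, one day late. Seen on Day 54, the early edge of the ±2-day window: Day 57 under A (three days late), Day 55 under B. Seen on Day 58: max(57, 58) = 58 under A, which is correct, and Day 59 under B.

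**ABPM subgroup**

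The last study visit can be Visit 10, the day after Visit 9, and the schedule marks no clinic dosing there. The second candidate can then also be a day late.

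**The case against.** The rule is a fallback. The eCRF asks for the last-dose date, Protocol 9.1.5 also has the date and time of the dose before each clinic blood pressure recorded, and Protocol 12.1 provides for queries on missing data. Missing dates should be few and mainly in subjects lost to follow-up with no ET visit, for whom a full interval is a defensible assumption. This stands, and it limits the size of the point.

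The later-of construction also has a purpose: on the scheduled reading it dates a late completer correctly (Day 58 above). This stands too, and it rules out simply switching to the earlier of the two dates.

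A reader might infer that no dose can ever follow Visit 9. The protocol does not support that. Section 9.3.8 keeps an ABPM subject on treatment when the final recording fails, with a repeat within 3 days.

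The downstream harm is also easy to overstate. Routine adverse event collection ends 14 days after the last dose, and spontaneous collection of serious events at 30 days (Protocol 10.2.1.1). No laboratory test is scheduled after Visit 9/ET. The widened windows would therefore mostly be empty, apart from unscheduled follow-up.

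None of this makes the rule correct for a subject who attended an ET visit and returned the drug.

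**Conclusion.** The point holds as a minor defect. For a subject with a missing last-dose date who attends Visit 9/ET on or before the next scheduled visit day, the SAP gives a last dose after drug collection: by 1 to 14 days if the next visit is the scheduled one, by 1 day if it is the ET visit. An on-schedule completer is one day late.

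A reader might infer that adherent early withdrawals will be dropped from the PPS. That rests on the scheduled reading, with ET on Days 2–10, 15–20 or 29–30; on the actual-visit reading it occurs only for ET on Day 2. The SAP does not settle which reading applies.

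Nor do the documents support a claim that the primary comparison is distorted. SAP 7.9 accepts a post-baseline pressure only 20 to 28 hours after the previous dose, so off-drug readings drop out whatever the window. The PPS analysis is a sensitivity analysis, and the exposure and compliance tables are descriptive.

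The number affected is unknown. The planning dropout of 10% implies 0.10 × 600 = 60 early withdrawals, but only those with a missing date matter, and completers with a missing date are also touched, so 60 is context and not a bound. The compliance figures assume full adherence up to the ET visit day.

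**What to change.** Reword the fallback in SAP 7.8:

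- **Visit 9/ET took place:** impute the date on which double-blind drug was finally collected, or the recorded discontinuation date if that is earlier. Normally the collection date is the Visit 9/ET date. For an ABPM subject kept on treatment for a repeat recording, it is the later drug-return date.
- **No Visit 9/ET (lost to follow-up):** impute the last dispense date plus (scheduled next visit day − scheduled last visit day), without the extra 1. Drug dispensed on Day 14 then gives 14 + (28 − 14) = Day 28.
- State that the next visit day is the scheduled day.
- Do not use Visit 10 as the last-dose date unless dosing after Visit 9 is recorded.

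Do not take the minimum of the visit date and the existing interval date. Drug dispensed on Day 42 with the Week 8 visit on Day 58 would give Day 57, and drug dispensed on Day 40 with the visit on Day 56 would give 40 + 15 = Day 55, each a day early.

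With the fix, the Day 18 case is dated Day 18 and compliance is 72/72 = 100%; the on-schedule completer is dated Day 56. The cost is a few lines of SAP text and a small change to the derivation code, made before unblinding. No new data are needed: Protocol 8.6 already requires the date and amount of returned drug to be logged.

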8.1.3 Dose and Regimen

This is a phase 3, multicenter, randomized, double-blind, parallel-group, 8-week efficacy and safety study comparing TAK-491 and valsartan.

Subjects will be randomized to 1 of the following 3 therapy treatment groups as follows:

- TAK-491 40 mg QD (N=200).
- TAK-491 80 mg QD (N=200).
- Valsartan 160 mg QD (N=200).

Study medication will be packaged in a manner to maintain the blind.

CONFIDENTIAL

Placebo Run-in Period (Day-14 [Visit 2] to Day -1)

- Subjects will be dispensed one 2-week blister card and one bottle.
- Subjects will receive single-blind placebo tablets and placebo capsules.
- First dose will be given in-clinic at Day -14 (Visit 2).
- The daily oral administered dose will be two tablets from a blister card and two capsules from the bottle.

Treatment Period (Day 1 [Visit 5] through Week 8 / Early Termination [Visit 9])

- Subjects will receive blinded study medication and will be instructed to take their blinded study medication prior to their first meal of the day. Subjects will be dispensed one 2-week carton and one bottle at day 1 (Visit 5), at week 2 (Visit 6), week 4 (Visit 7), and week 6 (Visit 8).
- First dose will be given in-clinic at Day 1 (Visit 5).
- The daily oral administered dose will be two tablets from a blister card and two capsules from the bottle

Table 8.a describes the dose and tablet/capsule count that will be provided to each group.

Table 8.a Sponsor-Supplied Drug

Treatment Group		Treatment Description		
	Dose	Active	Placebo	
	Run-in QD	Zero active tablets/capsules	One placebo for 40 mg TAK-491 tablet, one placebo for 80 mg TAK-491 tablet, two placebo for 80 mg valsartan capsules	
A	40 mg TAK-491 QD	One 40 mg TAK-491 tablet	One placebo for 80 mg TAK-491 tablet, two placebo for 80 mg valsartan capsules	
В	80 mg TAK-491 QD	One 80 mg TAK-491 tablet	One placebo for 40 mg TAK-491 tablet, two placebo for 80 mg valsartan capsules	
C	160 mg valsartan QD	Two 80 mg valsartan O/E capsules	One placebo for 40 mg TAK-491 tablet, one placebo for 80 mg TAK-491 tablet	

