9.2 Monitoring Subject Treatment Compliance

Subjects will be required to bring study medication containers to each clinic visit, regardless of whether the study medication container is empty.

If a subject is persistently noncompliant with the study medication (<70% or >130% of the allocated medication for the period since the last visit), it may be appropriate to withdraw the subject from the study. All subjects should be reinstructed about the dosing requirement during study contacts. The authorized study personnel conducting the re-education must document the process in the subject source records.

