## 7.9.1 Primary Efficacy Endpoint

The primary efficacy endpoint, change from Baseline to Week 8 in trough sitting clinic SBP, will be analyzed using an analysis of covariance (ANCOVA) model, with treatment group as a fixed effect and baseline sitting clinic SBP as a continuous covariate. Estimates of treatment LS mean, differences in LS means between TAK-491 treatment groups and valsartan, p-value and 2-sided 95% CIs for the treatment difference will be determined from the framework of the ANCOVA model. For the primary analysis, the overall type 1 error rate of 0.05 will be controlled using the 4-step sequential test described below.

- Step 1: A test for non-inferiority of TAK-491 80 mg to valsartan 160 mg will be performed using a non-inferiority margin of 1.5 mm Hg. If the upper limit of the 2-sided 95% CI of the treatment difference (TAK-491 valsartan) is not greater than 1.5 then proceed to Step 2.
- Step 2: A test for non-inferiority of TAK-491 40 mg to valsartan 160 mg will be performed using a non-inferiority margin of 1.5 mm Hg. If the upper limit of the 2-sided 95% CI of the treatment difference (TAK-491 valsartan) is not greater than 1.5 then proceed to Step 3.
- Step 3: A test for significant difference between TAK-491 80 mg versus valsartan 160 mg will be performed at the 5% level. If the p-value is not greater than 0.05 then proceed to Step 4.
- Step 4: A test for significant difference between TAK-491 40 mg versus valsartan 160 mg will be performed at the 5% level.

Based on historical data, the observed placebo-corrected treatment effects on change from Baseline in clinic SBP for valsartan 160 mg once daily was -8.6 mm Hg [4]. Therefore, the non-inferiority margin was set conservatively at 1.5 mm Hg, which is less than one-third of the valsartan treatment effect. Accordingly, TAK-491 will be considered non-inferior to valsartan

when the upper limit of the 2-sided 95% CI of the treatment difference (TAK 491- comparator) is  $\leq$ 1.5 mm Hg.

The following sensitivity analyses will be performed for the primary endpoint (change from Baseline in trough sitting clinic SBP at Week 8):

- Conduct the described primary analysis in the PPS to explore the robustness of the primary efficacy result.

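### The SAP 7.8 compliance formula counts tablets only (2 a day) against an expected 4 a day, so as worded full adherence scores 50% and fails the 70–130% per-protocol rule

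*SAP*

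**What the plan says.** SAP 7.8 describes the daily regimen as follows: "Subjects are to take 2 tablets for TAK-491 (40 mg/80 mg) and matching placebo or 2 capsules for valsartan and matching placebo each day". It then defines overall compliance as 100 times the tablets dispensed less the tablets returned, over the tablets expected, with "expected number of tablets to be taken = [4*(date of last dose of medication - date of first dose of medication + 1" fixing the denominator. Capsules appear in neither part of the ratio. Subjects are then tabulated "in each of the following compliance categories: <70%, 70 to 130%, >130" per cent.

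The score is also used in SAP 7.3, where the fifth PPS exclusion reads "Subjects with compliance outside of the range 70%-130" per cent. The PPS in turn supports sensitivity analyses of the primary endpoint in SAP 7.9.1, beginning with "Conduct the described primary analysis in the PPS to explore the robustness of the primary efficacy result".

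Protocol 8.1.3 states the regimen differently from the SAP: "The daily oral administered dose will be two tablets from a blister card and two capsules from the bottle". Table 8.a in that section shows a double-dummy design in which each arm has two tablets and two capsules a day. In the valsartan arm the active drug is "Two 80 mg valsartan O/E capsules", and both tablets are placebo.

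**The concern.** The numerator and denominator count different things. A subject who takes everything uses two tablets a day, while the formula expects four. The preceding sentence does not repair this: 'or' implies two units a day, which conflicts with both the factor 4 and protocol 8.1.3.

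The result decides who is in a prespecified analysis set. Applied literally, PPS criterion 5 would exclude every fully adherent subject, and the compliance table would place them all below 70%. The PPS is used for three of the five sensitivity runs on the primary endpoint, in a trial whose first two confirmatory steps are noninferiority tests.

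There is a less visible risk. A programmer who sees the mismatch can mend it in two ways: pool both forms over 4 per day, or count tablets over 2 per day. Both give 100% at full adherence, but they disagree for a subject who uses the two containers unequally.

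**Working it through.** **Inputs**

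- Tablets per day, every arm: 2 (protocol 8.1.1.1, 8.1.3 and Table 8.a).
- Capsules per day, every arm: 2 (same places).
- Expected count: 4 × D, with D = last dose date − first dose date + 1 (SAP 7.8).
- Acceptable range: 70% to 130% (SAP 7.3 and 7.8).
- Regular tablet supply: 40 per card, one card at each of Day 1 and Weeks 2, 4 and 6 (protocol 8.1.1.1 and 8.1.3), so 4 × 40 = 160.

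**Where the factor 4 comes from**

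2 tablets + 2 capsules = 4 units a day. Neither form alone gives 4.

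**Score at full adherence**

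| What is counted | Formula | At D = 56 | Score |
|---|---|---|---|
| Tablets only (as worded) | 2D / 4D | 112 / 224 | 50.0% |
| Capsules only | 2D / 4D | 112 / 224 | 50.0% |
| Tablets and capsules | (2D + 2D) / 4D | 224 / 224 | 100.0% |

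D cancels, so these scores hold for any duration.

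**What the range means on the literal reading**

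- Lower limit: 0.70 × 4 = 2.8 unreturned tablets a day, and 2.8 / 2 = 140% of the prescribed number.
- Upper limit: 1.30 × 4 = 5.2 a day, and 5.2 / 2 = 260%.
- A subject who returns nothing from the regular supply scores 160 / 224 = 71.4% at 56 days and 160 / 232 = 69.0% at 58 days, which is within the +2-day Week 8 window.

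So, without replacement supplies, a subject finishing on schedule could reach the range only by returning almost no spare tablets.

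**Why the choice of repair matters**

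Take a hypothetical subject over 56 days with all 112 tablets and 45 of 112 capsules used:

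- Pooled: (112 + 45) / 224 = 157 / 224 = 70.1%, kept in the PPS.
- Tablets over 2D: 112 / 112 = 100%, kept.
- Capsules over 2D: 45 / 112 = 40.2%, excluded if capsules were judged alone.

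With 44 capsules the pooled score is 156 / 224 = 69.6%, and the subject is excluded.

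**Sensitivity runs that use the PPS (SAP 7.9.1)**

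The three listed items expand to five runs: last observation carried forward (LOCF) in the PPS; multiple imputation in the full analysis set and the PPS; observed cases in the full analysis set and the PPS. Three of the five are in the PPS.

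**The case against.** The best reply is that the constant is right and only the label is loose. The formula is for overall study drug compliance. Protocol 8.1.1 uses 'study medication' for tablets and capsules alike, and protocol 9.2 judges compliance as a share "of the allocated medication for the period since the last visit". Since no arm takes four tablets a day, the 4 can only have come from adding the two forms. This is a good argument about intent, and I accept it as the likely one. It does not make the text correct: the SAP names tablets and capsules as separate things in the sentence just before the formula, joins them with 'or', and then counts only one of them.

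The second reply is that the error could hardly pass unnoticed. Protocol 13.1 provides a blinded data review, protocol 13.1.1 requires PPS exclusions to be identified before unblinding, SAP 7.3 tabulates exclusions by criterion, SAP 7.1.2 calls for derived dataset specifications, and accountability data are listed. A nearly empty PPS would be seen. This stands as mitigation and lowers the practical risk. None of these places gives the correct count, however, so they would reveal the symptom without settling which repair applies.

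Third, the reach is limited. The full analysis set is primary, and SAP 7.9 runs PPS analyses only where appropriate. That also stands.

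**Conclusion.** The concern holds. As worded, the compliance formula in SAP 7.8 gives 50.0% for full adherence at any duration, and PPS criterion 5 would then exclude every fully adherent subject. With tablets and capsules both counted, the same factor 4 gives 100.0% and the rule works.

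This is an error of wording and not of the constant. The conclusion rests on the protocol 8.1.3 regimen applying to all three arms, as Table 8.a shows. The documents do not reveal how the calculation was or will be programmed, so an actual effect on results cannot be claimed. The primary analysis and the four-step sequential test are unaffected. The text should be corrected because it defines membership of a prespecified analysis set.

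**What to change.** In SAP 7.8:

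1. Change 'or' to 'and' in the sentence on the daily regimen, so that it agrees with protocol 8.1.3.
2. Define compliance as 100 × (tablets and capsules dispensed − tablets and capsules returned) / (4 × days on drug), naming both forms in numerator and denominator.
3. Carry the same definition into the derived dataset specifications.

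PPS criterion 5 and the compliance categories need no change. The cost is a few words before unblinding, plus the SAP amendment that SAP 3.0 requires for such changes.

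Optionally, report tablet and capsule compliance separately as well, each over 2 × days, because a pooled score can hide poor use of one container. In the hypothetical subject above, a valsartan-arm patient would stay in the PPS on about 40% of the active drug. This needs returns recorded by container, which the documents do not show, and the correction does not depend on it.
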